### **5.3 Analysis of Clinical Data**

This registry is not hypothesis driven. The limitation of the design for this registry is that there are no pass/fail criteria from a statistical hypothesis testing.

Descriptive statistics will be generated for all endpoints using a 1-sided 95% confidence interval. Participant data will be quantified. For quantitative parameters, descriptive statistics will be reported: number, mean, standard deviation (SD), minimum, median and maximum values. For categorical variables, frequency and percentage will be reported. The primary endpoint will be compared to historical data using one-way analysis of variance.

Subset analysis may be performed for participants who have undergone neoadjuvant therapy.

Endpoint analysis will be performed on the PP analysis set. Descriptive data and adverse event analysis will be performed on the ITT analysis set.

Full analysis will be described in the statistical analysis plan and specified in the final report. No interim analysis is planned.

The Sponsor will perform data management and statistical analysis. Statistical analyses will be performed using the Statistical Analysis System (SAS) or other widely accepted statistical software.

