### **4.2 Endpoints**

The primary endpoint is the number of patient visits to the breast center for invasive procedures from the time of biopsy to surgery. The primary endpoint will be compared to historical controls. It is expected that there will be a mean reduction of at least one (1) visit for invasive procedures.

The secondary endpoints are defined below:

1. Device success: percent successful localization, detection and retrieval.
2. Device safety: rate of device-related adverse events.
3. Procedural success: absence of close margins (<2mm), positive margins (tumor on ink) or requirement for re-excision.
4. Duration (days) from diagnosis to surgery and biopsy to surgery.
5. Radiologist assessment: ease of placement; ability to position reflector in desired location; scheduling flexibility; visibility on ultrasound/ mammography (immediate and late); artifact (Tomo/MRI if applicable).
6. Surgeon assessment: ease of detection; ease of device retrieval.
7. Participant satisfaction questionnaire: anxiety; convenience; pain; overall experience compared to expectation
8. Process improvement with implementation of same-day biopsy and SCOUT® Reflector placement.

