#### **4.5 Design**

This is a single-arm, multicenter, non-randomized cohort study that will include five hundred (500) participants scheduled to undergo a biopsy of a breast lesion at participating Canadian and US study centers.

The expected duration of the trial is 12-18 months. Enrollment is expected to take approximately 12 months.

The primary endpoint of this cohort will be compared to historical controls (standard of care visits).

The registry is divided into three periods:

1. Inclusion Period: from registry eligibility screening until reflector insertion;
2. Device Period: from reflector insertion at biopsy to removal at surgery;
3. Outcomes Period: from completion of surgery to pathology report of outcomes.

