## 5. Data Analysis & Statistics

### 5.1 Sample Size Calculation

No formal sample size calculation has been performed. Five hundred (500) participants will be included in this registry. This sample size has been selected to adequately support a multi-center experience reflective of the Canadian and US healthcare system and associated workflow.

Further, the Canadian Agency for Drugs and Technologies in Health (CADTH) assessed the evidence of a competitive device and noted the requirement for a cohort size greater than 200 in order to draw conclusions of effectiveness. It is estimated that this sample size will result in a robust data set.

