### 5.2 Point of Inclusion

A patient is considered enrolled in the registry as soon as they:

1. Have provided signed consent agreeing to be part of this registry; and
2. Undergo the insertion of the SCOUT® Reflector at the time of biopsy

*Note- If a patient has given consent but the Reflector is not inserted at biopsy, the patient will not receive a participant number and will not be considered as enrolled in the registry. No patient data will be collected.*

The intent-to-treat (ITT) population includes all participants in whom the SCOUT® Reflector has been inserted. Any participants who have a reflector inserted and do not undergo surgery will be exited from the registry using a study completion form. The occurrence of this scenario is expected to be low ( $\leq 10\%$ ). Reasons may include:

1. Benign concordant biopsy results.
2. Participant death prior to surgery due to metastases.
3. Lesion is metastatic from another location.
4. Participant declines surgery.
5. Participant is ineligible for surgery.

The per protocol (PP) population will include all participants in whom a SCOUT® Reflector has been inserted and who subsequently undergo breast surgery.

Participation in the registry will be considered complete after surgery, documentation of surgical outcomes and completion of the Participant Assessment Questionnaire. This will be documented on a study completion form. It is expected the duration of each participant will be approximately  $<7$  months and will vary based on each participant's treatment plan.

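### The one-way ANOVA on visit counts assumes a common variance that the plan gives no ground for; an unequal-variance (Welch) comparison is safer at almost no cost

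*Protocol*

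**What the plan says.** Protocol 4.2 defines the outcome as a count: "The primary endpoint is the number of patient visits to the breast center for invasive procedures from the time of biopsy to surgery". It adds an expectation: "It is expected that there will be a mean reduction of at least one (1) visit for invasive procedures". Protocol 5.3 names the method: "The primary endpoint will be compared to historical data using one-way analysis of variance". SAP sections 7 and 8 repeat that sentence and add no variance check, alternative or fallback, although Protocol 5.3 leaves the full analysis to the SAP.

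On group sizes, Protocol 5.1 states: "No formal sample size calculation has been performed. Five hundred (500) participants will be included in this registry". Protocol 5.3 restricts the endpoint analysis: "Endpoint analysis will be performed on the PP analysis set". Protocol 5.2 expects at most 10% of participants to have a reflector inserted and not reach surgery. The historical group is described in Protocol 4.5 only as standard-of-care visits, with no source, size, mean or SD.

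Protocol 5.3 also says that the registry is not driven by a hypothesis and has no statistical pass/fail criterion. Its one-sided 95% confidence intervals are attached to the descriptive statistics; no interval for the difference from the historical data is specified.

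**The concern.** A standard one-way ANOVA pools the within-group variances into a single estimate. That is sound if the variances are equal, or nearly harmless if the groups are of similar size. The plan secures neither condition.

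There is some reason to expect different spreads. Enrolment has a second condition besides consent: "Undergo the insertion of the SCOUT® Reflector at the time of biopsy". The per-protocol set then keeps only those who reach surgery, so SCOUT counts are conditioned on one pathway. The protocol's account of usual care covers several routes: a wire placed the day before or on the day of surgery (2.2.1) and a radioactive seed placed days ahead (2.2.2). These could produce different visit counts. That is inference from the design, not a documented fact.

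Because there is no pass/fail test, the estimated reduction and its uncertainty are the result. A biased SE would misstate the precision of the reduction and the p-value of any difference well below one visit. SAP section 12 plans to report p-values to three decimals.

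**Working it through.** The plan has no figure of its own to reproduce: it gives no power, test level, SD or historical sample size.

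**Inputs**
- SCOUT per-protocol size: 500 enrolled, at most 10% lost, so 500 × 0.90 = 450 up to 500 (Protocol 5.1 and 5.2). I use 450.
- SCOUT SD: not given. Assumed 0.3, with 0.5 as a variant.
- Historical size and SD: not given. Assumed sizes 50 to 2000 and SDs 0.3 to 0.9.
- Test level: not given. Two-sided 5% assumed for illustration. The SE ratio does not depend on this choice.

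**Formulas** (group 1 SCOUT, group 2 historical)
- Pooled variance: sp² = [(n1−1)s1² + (n2−1)s2²] / (n1+n2−2)
- Pooled SE (ANOVA): √[sp²(1/n1 + 1/n2)]
- Welch SE: √(s1²/n1 + s2²/n2)
- Actual large-sample error of a nominal 5% test: 2[1 − Φ(1.96 × pooled SE / Welch SE)]

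**One case in full** (450 with SD 0.3; 100 with SD 0.6)
- sp² = (449 × 0.09 + 99 × 0.36) / 548 = 76.05 / 548 = 0.1388
- Pooled SE = √[0.1388 × (1/450 + 1/100)] = 0.0412
- Welch SE = √(0.09/450 + 0.36/100) = √0.0038 = 0.0616
- Ratio = 0.67; actual error = 2[1 − Φ(1.31)], about 19%

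**Varying the control SD** (SCOUT 450, SD 0.3; 100 controls)

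| Control SD | Pooled SE | Welch SE | Ratio | Actual error |
|---|---|---|---|---|
| 0.3 | – | – | 1.00 | 5% |
| 0.4 | 0.035 | 0.042 | 0.84 | 10% |
| 0.6 | 0.041 | 0.062 | 0.67 | 19% |
| 0.9 | 0.052 | 0.091 | 0.57 | 26% |

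**Varying the control size** (SCOUT 450, SD 0.3; control SD 0.6)

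| Controls | Pooled SE | Welch SE | Ratio | Actual error |
|---|---|---|---|---|
| 50 | 0.0509 | 0.0860 | 0.59 | 25% |
| 200 | 0.0353 | 0.0447 | 0.79 | 12% |
| 450 | 0.0316 | 0.0316 | 1.00 | 5% |
| 500 | 0.0313 | 0.0303 | 1.03 | 4.3% |
| 1000 | 0.0298 | 0.0237 | 1.26 | 1.4% |
| 2000 | 0.0291 | 0.0195 | 1.49 | 0.4% |

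If SCOUT is the more variable group (SD 0.5 against 0.3), the directions reverse: ratio 1.49 with 50 controls and 0.74 with 2000.

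**Simulation check.** Visit counts of 1, 2 or 3 were simulated with equal means and SDs of about 0.32 and 0.60. The pooled test rejected in 23.4%, 17.7%, 11.3%, 5.0%, 1.1% and 0.6% of runs for 50, 100, 200, 450, 1000 and 2000 controls. Welch stayed between 4.5% and 5.1%.

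**At the expected one-visit reduction.** With 100 controls and control SD 0.6, t is 1/0.0412 = 24.3 pooled and 1/0.0616 = 16.2 Welch. With control SD 0.9, Welch t is 1/0.0911 = 11.0. Even with 50 controls and SD 0.9, the Welch SE is √(0.0002 + 0.0162) = 0.128 and t is 7.8.

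**What can change.** In the 100-control, SD 0.6 case the two-sided 95% half-width is 1.96 × 0.0412 = 0.08 pooled and 1.96 × 0.0616 = 0.12 Welch. An observed reduction of 1.10 would have a lower limit of 1.02 with the first and 0.98 with the second.

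**The case against.** The strongest objection is that unequal variance is nowhere documented. A reader might infer that SCOUT counts are nearly constant by design while historical counts are not, so that the SE is wrong whenever the groups differ in size. The documents do not support that. Usual care could be just as regular: a biopsy visit plus one localization. If the reflector removes one fixed visit and nothing else changes, the SDs are equal and the pooled SE is right at every group size. SCOUT counts can also vary: SAP 7.1 takes the endpoint from a form for additional visits, SAP 7.3 foresees back-up wire bookings, and SAP 6.3 foresees a neoadjuvant subset. This part of the objection stands, and the point is therefore conditional.

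Second, the consequence is limited. No pass/fail decision depends on the test level, a one-visit reduction is detected under either SE, and the plan specifies neither an interval for the difference nor a criterion that the interval exclude one visit. This stands too and sets the severity. It does not remove the point: in a descriptive registry the stated precision is what readers will use.

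Third, the undefined comparator is the larger gap. If the historical reference is only a published mean or a fixed number, neither ANOVA nor Welch can be run. That is correct, and the fix has to cover that case.

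**Conclusion.** The point holds as a minor one. The plan commits to a pooled-variance method without giving any SD, any historical sample size or any fallback. If SDs and sizes both differ, the SE is biased, in a direction set by which group is larger. Under the assumed values the pooled SE ranges from 0.57 of the Welch SE (100 controls, SD 0.9) to 1.49 times it (2000 controls, SD 0.6). At 450 against 500 the discrepancy is only a few percent, and with equal SDs there is none. All SDs and control sizes here are assumptions, and 0.9 against 0.3 is at the extreme end.

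A reader might go further and conclude that the registry's main finding is at risk. It is not: at the expected one-visit reduction, t is far beyond any conventional threshold in every case worked. What is exposed is the SE, any interval placed around the reduction, and p-values for smaller differences.

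**What to change.** In Protocol 5.3 and SAP sections 7 and 8, replace the one-way ANOVA with a Welch (unequal-variance) comparison of mean visits, and report the mean difference with the Welch confidence interval, stating whether it is one- or two-sided. This needs a mean, SD and sample size for the historical group, so the SAP should name the source and confirm that these exist. If the historical reference turns out to be only a fixed number, report a one-sample confidence interval for the SCOUT mean against it.

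The change to the method is one sentence in each place and a software option. It needs no further SCOUT data and loses almost nothing if the variances prove equal. The historical summary figures are needed for the planned ANOVA in any case.

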6.3 Covariates and Subgroups

Subset analysis will be performed for participants who have undergone neoadjuvant therapy (if applicable). Endpoints will be assessed separately and compared to the full cohort for safety, performance and utility.

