7.2 Derived variables

Variable	Definition	Unit
Duration (assessment to surgery) (DA_S)	Difference between assessment date and surgery date	Number of days
Duration (biopsy to assessment) (DB_S)	Difference between biopsy date and surgery date	Number of days
Implementation of same day biopsy	Percent of cases with DB_S=0 (start of site participation to study end)	Percent
Operative time	Difference between stop and stop times	Minutes

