7.6 Treatment Variables

Variable	Type of data/ unit
Neoadjuvant therapy	Nominal
Duration of neoadjuvant therapy	Calculation (start- stop date)/ days
Number of visits for invasive procedures	Continuous

8 Utility Analyses

Number of visits for invasive procedures will be reported as: number, mean, standard deviation (SD), minimum, median and maximum values.

The primary endpoint will be compared to historical data using one-way analysis of variance.

9 Performance Analyses

Device and procedure success will be calculated as a percentage of the total number of cases, as well as the total number of reflectors used in the study.

10 Safety Analyses

- All reported adverse events will be categorized and described.
- Frequency and/ or percentage will be reported
- Adverse device effects (ADE) rates will be calculated separated
- ADEs will be sub-classified as appropriate
- Each participant will only be counted once and any repetitions will be ignored; the denominator will be the total population size
- Serious Adverse Events: A table of all anticipated and unanticipated serious adverse events, grouped by organ system, with number and frequency of such events in each arm/group of the clinical study. (See Adverse Events definition below).
- Other (Not Including Serious) Adverse Events: A table of anticipated and unanticipated events (not included in the serious adverse event table) that exceed a frequency threshold (for example, 5 %) within any arm of the clinical study, grouped by organ system, with number and frequency of such events in each arm/group of the clinical study.

11 Satisfaction Analyses

Clinician and participant satisfaction assessment data will be categorized and reported as frequency data.

12 Reporting Conventions

P-values ≥ 0.001 will be reported to 3 decimal places; p-values less than 0.001 will be reported as " <0.001 ". The mean, standard deviation, and any other statistics other than quantiles, will be reported to one decimal place greater than the original data. Quantiles, such as median, or minimum and maximum will use the same number of decimal places as the original data.

13 Summary of Changes to the Protocol and/or SAP

n/a

14 References

CADTH, 2019: CADTH rapid response report: summary with critical appraisal. Magnetic seed localization for soft tissue lesions in breast patients: Clinical effectiveness, cost- effectiveness, and guidelines.

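### No planned analysis relates reflector detection or retrieval success to time in place, so a loss of performance at long biopsy-to-surgery intervals could be diluted in the pooled rate

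*Protocol*

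**What the plan says.** Protocol 4.5 runs the Device Period from insertion at biopsy to removal at surgery, so time in place is the biopsy-to-surgery interval. Protocol 4.2 lists device success (localization, detection, retrieval) and that interval as two separate secondary endpoints.

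- **Device success.** SAP section 9: "Device and procedure success will be calculated as a percentage of the total number of cases", and also over all reflectors used. Protocol 5.3 and SAP 6.2.1 place endpoint analysis on the per-protocol set, meaning participants who go on to surgery.
- **Interval.** SAP 7.2 defines DB_S as "Difference between biopsy date and surgery date", in days. The row label, however, reads biopsy to assessment, and the next row uses DB_S = 0 to define same-day biopsy.
- **Neoadjuvant subset.** Protocol 5.3: "Subset analysis may be performed for participants who have undergone neoadjuvant therapy". SAP 6.3 is firmer: "Subset analysis will be performed for participants who have undergone neoadjuvant therapy (if applicable", and it compares the subset's endpoints, performance included, with the full cohort.
- **Other split.** SAP 6.5.2 compares endpoint data between sites.
- **Precision.** Protocol 5.3: "Descriptive statistics will be generated for all endpoints using a 1-sided 95% confidence interval".

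Protocol 5.2 expects each participant's duration to be under about 7 months and to vary with the treatment plan. Detection, retrieval and the relevant dates are all recorded per participant (Protocol 4.7 and 4.9).

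**The concern.** Placement at biopsy, as opposed to shortly before surgery, makes time in place long and variable. Protocol 2.2.2 quotes a mean of 4.0 days and a median of 2 days from seed placement to surgery, and treats delay to surgery as the reason seeds are unsuitable at biopsy. Whether the reflector performs as well after a long interval as after a short one therefore bears directly on the secondary objective of evaluating performance.

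The plan holds both variables and never puts them together. The neoadjuvant subset does not fill the gap, for three reasons. It mixes time in place with treatment-induced change in the lesion. It leaves out long waits without neoadjuvant therapy. Its comparator contains the subset itself, which shrinks any contrast. A high pooled rate made up mostly of short intervals could then be taken to apply to long ones without having been checked.

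**Working it through.** **Inputs from the documents.** Enrolment is 500: "Five hundred (500) participants will be included in this registry". There is no planning figure to reproduce: "No formal sample size calculation has been performed". Of participants with no surgery after insertion, Protocol 5.2 says "The occurrence of this scenario is expected to be low" (at most 10%), so the operated set is at least 500 × 0.90 = 450.

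**Assumed inputs.** The share *s* of long intervals and the failure rates at short and long intervals are not in the documents. The figures below are illustrations.

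**Step 1: dilution in the pooled rate.** Pooled failure = *s* × 5% + (1 − *s*) × 0.5%.

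| *s* | Long / short (n) | Pooled failure | Pooled success | Expected failures in 450 |
|---|---|---|---|---|
| 10% | 45 / 405 | 0.95% | 99.1% | 4.3 |
| 20% | 90 / 360 | 1.40% | 98.6% | 6.3 |
| 40% | 180 / 270 | 2.30% | 97.7% | 10.4 |

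Success at long intervals is 95% in every row.

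Other assumed rates behave the same way. With 99% success at short and 90% at long intervals, pooled success is 98.1%, 97.2% and 94.5% for *s* = 10%, 20% and 50%. With 99% and 95%, it runs from 98.6% (*s* = 10%) to 97.0% (*s* = 50%).

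**Step 2: what subset against full cohort does.** Take the case most favourable to the proxy, in which the neoadjuvant participants are exactly the long-interval ones. The contrast is then (1 − *s*) × true difference. A true gap of 5% − 0.5% = 4.5 points shows as 4.05, 3.6 and 2.7 points for *s* = 10%, 20% and 40%.

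**Step 3: long waits outside the subset.** Suppose 90 of 450 intervals are long and only 45 of those participants had neoadjuvant therapy, with no other neoadjuvant cases. Failure among the remaining 405 is (45 × 5% + 360 × 0.5%) / 405 = (2.25 + 1.80) / 405 = 1.0%. They read as 99.0% success, with 45 long waits at 95% inside that figure.

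**Step 4: what a split could show.** One constructed outcome is 5/90 failures at long intervals (5.6%, two-sided exact 95% CI 1.8% to 12.5%) against 2/360 at short ones (0.6%, 0.1% to 2.0%), Fisher p = 0.004. Pooled, it is 7/450, or 98.4% success.

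Such clarity is not assured. With 0.5% failure at short intervals, the chance that Fisher's test gives p < 0.05 is:

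| Long-interval failure | *s* = 10% | *s* = 20% | *s* = 40% |
|---|---|---|---|
| 5% | 50% | 74% | 87% |
| 2% | 13% | 22% | 25% |

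Precision in a small stratum is limited. With no failures at all, the one-sided 95% lower limit for success, 0.05^(1/n), is 93.6% for n = 45, 96.7% for n = 90 and 99.3% for n = 450.

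**The case against.** The registry is descriptive, without a hypothesis test, and its primary endpoint is visits. Device success is one of eight secondary endpoints. Several stronger readings are tempting, and the documents do not support them.

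- **That the neoadjuvant analysis is optional.** Only the protocol's wording allows this. Protocol 5.3 defers the full analysis to the SAP, and SAP 6.3 plans it for performance. What remains is a difference in wording to reconcile.
- **That a loss would be hidden.** This goes too far. Migration, inaccurate location detection and any device deficiency are reportable (Protocol 7.2). Potentially device-related events go to an independent adjudicator (Protocol 7.4). Sites are compared. With perhaps 4 to 10 failures, each could be reviewed alongside its dates. None of this sets failures against the number of participants at each interval, however.
- **That time in place runs to 7 months.** That figure is expected participation, which includes pathology and a questionnaire allowed up to 2 weeks after surgery. It is only an upper guide.
- **That performance does fall with time.** No passage reports this. The seed passage concerns a radioactive source and does not say that detection weakens. Protocol 3.1 describes the reflector as intended for placement beyond 30 days.

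The objection that few failures make modelling fragile stands in full. The descriptive character of the registry does not answer the point, because the request is itself a descriptive table.

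**Conclusion.** The gap is real and modest. Detection and retrieval are never related to days in place, and the one clinical subset is a confounded, partial and overlapping proxy. A time-related loss could be diluted in the headline rate, and no analysis is planned to look for it.

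The size depends wholly on assumed rates and on 450 operated participants. In the main illustration a true 95% at long intervals sits beneath a pooled 97.7% to 99.1%. These are not predictions, and a split would not reliably detect a small loss. No alpha, power or sample-size figure is affected. The change is worth making because it costs little and serves the stated performance objective.

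**What to change.** 1. In SAP 7.2, correct the DB_S row so that label and definition agree, and revisit the same-day biopsy row, which uses DB_S = 0.
2. In SAP 6.3 and section 9, pre-specify one descriptive table of detection and retrieval success by days from insertion to surgery, in categories fixed before the data are seen (for example ≤30, 31–90, >90). Give numerators, denominators and exact 95% intervals, and state whether these are one-sided, as planned elsewhere, or two-sided. Show it for all operated participants and again for those without neoadjuvant therapy.
3. Compare neoadjuvant with non-neoadjuvant participants as non-overlapping groups, in place of subset against full cohort.
4. Reconcile *may* in Protocol 5.3 with *will* in SAP 6.3.
5. Omit a logistic model on days in place, or label it exploratory, because few failures are expected.

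The cost is SAP wording and one table from dates and outcomes already collected. The downside is wide intervals in the longest stratum, more so without neoadjuvant participants. The table should be presented as description and not as a powered test.
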